### 8.2 Statistical Methods

#### 8.2.1 Efficacy Analyses

CFU values will be calculated as per the Bacterial Enumeration methods above. Individual plate CFU counts that are zero will be treated as 0.5 for further calculations. Changes from baseline will be calculated separately for each subject and for each of the three non-baseline sites by taking the baseline  $\log_{10}$  CFU/cm^2 values and then subtracting the  $\log_{10}$  CFU/cm^2 values for the samples taken after the baseline. Therefore, a subject who completes all treatments and passes all baseline requirements will have 4 (sites) \* 3 (post-application samples per site) = 12 changes from baseline reported. Responder status will be calculated for each reported  $\log_{10}$  CFU/cm^2 reduction. The sites will be considered responders based on the sample time and body area:

For the groin at 30 seconds or 10 minutes, a  $\log_{10}$  CFU/cm^2 reduction  $\geq 3.0$  is considered a responder.

For the abdomen at 30 seconds or 10 minutes, a  $\log_{10}$  CFU/cm^2 reduction  $\geq 2.0$  is considered a responder.

For either the groin or the abdomen at 6 hours, a  $\log_{10}$  CFU/cm^2 value less than baseline (i.e., a  $\log_{10}$  CFU/cm^2 reduction  $> 0$ ) is considered a responder.

Responder statuses will be grouped by body area, sample time, and test substance. Exact confidence intervals will be calculated for responder rates. The primary efficacy goal is to have the 95% confidence intervals for the responder rate at 10

minutes to be  $\geq 70\%$ . The secondary efficacy goals are to have the 30 second and 6 hour 95% confidence intervals for the responder rates to be  $\geq 70\%$ .

Differences in responder rates between treatments and their confidence intervals will be calculated using asymptotic (approximate) methods. If differences in responder rates are not reliable based on approximate methods, which happens when rates are near either 100% or 0%,  $\log_{10}$  CFU/cm^2 confidence intervals for the differences will be used for comparison instead.

Two-sided confidence intervals for  $\log_{10}$  CFU/cm^2 changes from baseline will also be calculated. These calculations will use an ANOVA model with subject as a random variable and test substance as a fixed variable. Body area (abdomen or groin) will be a fixed variable. Sample times (30 seconds, 10 minutes, or 6 hours) will be calculated separately using identical models. Differences in  $\log_{10}$  CFU/cm^2 reductions will be calculated based on the same model.

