#### Left/Right Balance

The application will be randomized so that each treatment is used on an equal number of left and right sides of the body.

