#### Site and Sample Time Balance

Within each anatomical site, sampling order will be randomized for baseline, 30 second, 10 minute, and 6 hour samples based on the statistical consultant's randomization plan.

The randomization plan has been updated [REDACTED]

The Investigator is responsible for ensuring that the randomization is followed. A basic outline of a randomization schedule for the abdominal and groin sites is provided in Appendix 14.4. The final randomization schedule will be prepared before the initial treatment. The test and control articles will be labeled with the appropriate codes as designated by the study randomization.

Subjects will be identified by their initials, a screening ID number, and a subject number corresponding to each body region in the study for which they qualify. Subject numbers will not be assigned until a subject has passed the screening criteria, including baseline bacterial counts (at least  $1.0 \times 10^5$  CFU/cm^2 in the groin and at least  $1.0 \times 10^3$  CFU/cm^2 on the abdomen). Subjects whose abdominal and groin regions qualify will be assigned the subject number. Therefore, for each of the participating subject will be assigned two identification numbers.

- Screening subjects will be assigned numbers ranging from 9001 to 9999.
- Subjects to be treated (including treatment day baseline collection) will be assigned sequential numbers ranging from 0001 up to the total number of test subjects treated.

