**Protocol Amendment(s): (continued)**

- The following paragraphs are added to end of Section 8.2.1 Efficacy Analysis of the protocol:

Average Treatment Effect (ATE) will be estimated from a linear regression of posttreatment bacterial count ( $\log_{10}$  scale) on the additive effect of a treatment indicator and the baseline or pretreatment measurement ( $\log_{10}$  scale). ATE will be calculated for the 10 minute samples separately for each product and each body area. This will generate 3 (products) \* 2 (body areas) \* 1 (post-treatment time point) = 6 ATEs, one each for each combination of product and body area at 10 minutes. The ATEs will be compared as follows:

- a. ZuraPrep™ will be compared to the ChloraPrep®. To show effectiveness, ZuraPrep™ should be non-inferior to ChloraPrep® with a 0.5 margin. Specifically, the upper bound of the 95% confidence interval of the ATE of ChloraPrep® minus the ATE of ZuraPrep™ should be less than or equal to 0.5.
- b. ZuraPrep™ will be compared to ZuraPrep™ vehicle. To show effectiveness, ZuraPrep™ should be superior to ZuraPrep™ vehicle by a 1.2 margin. Specifically, the lower bound of the 95% confidence interval of the ATE of ZuraPrep™ minus the ATE of ZuraPrep™ vehicle should be greater than or equal to 1.2.

The same ATE calculations will be performed for the 30 second time point, but the results are for informational purposes only.

[REDACTED]

[REDACTED]

Date Issued: 10/26/17 [REDACTED]	Laboratory Project Identification No. 865-105 Zurex Pharma, Inc. Project No.: ZX-ZP-0073		
STUDY TITLE: Pivotal Clinical Evaluation of the Antimicrobial Effectiveness of Topically Applied ZuraPrep™	STUDY DIRECTOR: M. [name] CCRP Signature [REDACTED] Date 10/26/17		
TEST AND CONTROL ARTICLES: ZuraPrep™ [REDACTED] ZuraPrep™ Vehicle (Without Isopropyl Alcohol) [REDACTED] ChloraPrep® [REDACTED] (Scrub Teal® Tint)	ID/LOT NO. [REDACTED]	DATE RECEIVED: [REDACTED]	DS NO. [REDACTED]
PERFORMING DEPARTMENT(S): Clinical Laboratory	STORAGE CONDITIONS: Location: [REDACTED]  Dark  Ambient Room Temperature  Desiccator  Freezer  Refrigerator  Other		

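### The section 8.2.1 ANOVA of log10 change from baseline has no Treatment Day baseline covariate and ignores the randomised sampling position, so its intervals may be wider than necessary

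*Combined protocol and SAP*

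**What the plan says.** Section 8.2.1 defines the change as baseline log10 CFU/cm² minus the later value, and gives the model for its confidence intervals: "These calculations will use an ANOVA model with subject as a random variable and test substance as a fixed variable". It adds "Body area (abdomen or groin) will be a fixed variable" and "Sample times (30 seconds, 10 minutes, or 6 hours) will be calculated separately using identical models". Differences between products come from the same model. No other term is named.

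This ANOVA has two uses. Under Study Validity (sections 3.2 and 6.1), responder rates at 6 hours are expected to be near 100% in all arms, so log10 reductions are to show that the active products beat the vehicle. Section 8.2.1 also turns to log10 intervals when the approximate methods for responder-rate differences are unreliable.

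On the design side, section 3.3 states "The application will be randomized so that each treatment is used on an equal number of left and right sides of the body" and "Within each anatomical site, sampling order will be randomized for baseline, 30 second, 10 minute, and 6 hour samples". Sections 5.1.2.1.1 and 5.1.2.1.2 give each test area four numbered sampling sites: one for baseline and one for each post-application time.

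Amendment 6 adds a separate regression to section 8.2.1 for the average treatment effect (ATE). It regresses post-treatment log10 count "on the additive effect of a treatment indicator and the baseline or pretreatment measurement". This regression carries the 0.5 non-inferiority and 1.2 superiority margins.

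**The concern.** A change score fixes the coefficient of the baseline at 1. If the post-treatment count follows baseline less closely than that, part of the baseline variation stays in the residual and widens every interval from the ANOVA. Adding the baseline as a covariate lets the data choose the slope.

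Position raises a similar question. The baseline and post-application samples come from different spots, so any real difference between spots enters each change twice, and the model does not remove it.

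What is at stake is precision, mainly in the 6-hour comparison with vehicle. The vehicle arm is the smallest, with 64 sites per body area against 320 for each active product.

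**Working it through.** **The plan's own figure.** Section 8.3 gives 267 per active product (70% against 77.8%, 80% power). With two-sided 0.05, n = ((1.96·√(0.7·0.3) + 0.842·√(0.778·0.222))/0.078)² = 256, or 269 with a continuity correction. The exact check at n = 267 requires 202 responders for the lower 95% bound to reach 70%, with power 82.1%. The figure is therefore reproduced closely. It sizes the responder-rate endpoint, which uses no regression model, so nothing below changes it. The visible documents give no figure for the width of a log10 interval.

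**Pairing.** The 352 subjects give 704 sites per body area = 320 + 320 + 64. Solving for the pairs gives 288 test–reference, 32 test–vehicle and 32 reference–vehicle.

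**Baseline covariate.** Let b be the slope of post-treatment on baseline log10 count, SDb the baseline standard deviation and s the residual standard deviation given baseline. Then

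SE(change score) / SE(baseline-adjusted) = √(1 + (1 − b)²·SDb²/s²).

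None of the three inputs is in the documents. I assume SDb 0.3 to 0.7 and s 0.8 to 1.3. As a guide to SDb, both baseline windows in Table 3.2 are 2.5 log10 wide, and a uniform spread over 2.5 has standard deviation 2.5/√12 = 0.72.

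| Slope b | Smallest ratio (SDb 0.3, s 1.3) | Largest ratio (SDb 0.7, s 0.8) |
|---|---|---|
| 1 | 1.00 | 1.00 |
| 0.5 | √(1 + 0.25·0.09/1.69) = 1.01 | √(1 + 0.25·0.49/0.64) = 1.09 |
| 0 | √(1 + 0.09/1.69) = 1.03 | √(1 + 0.49/0.64) = 1.33 |

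**In log10 units.** Assume a standard deviation of 0.9 for the change, and ignore pairing. The 95% half-width for 320 against 64 sites is 1.96·0.9·√(1/320 + 1/64) = 0.24. Dividing by 1.09 gives 0.22, a saving of 0.02. Dividing by 1.33 gives 0.18, a saving of 0.06.

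**Side.** A left–right shift common to baseline and post-treatment counts cancels in the change score. Simulating the paired design with a side term added gave no change in width.

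**Position.** Suppose the layouts on a subject's two sides are independent and the position standard deviation is τ. Position adds about 2τ² to the variance of each change, so removing it multiplies the width by about 1/√(1 + 2τ²/s²). With s = 1.0 this gives 0.99, 0.96 and 0.92 at τ = 0.1, 0.2 and 0.3. Simulations of the 288/32/32 design, which include the cost of estimating the terms, gave:
- τ = 0: about 1% wider (1–2% of variance)
- τ = 0.1: 0–1% narrower
- τ = 0.2: 3–4% narrower
- τ = 0.3: 6–9% narrower, depending on how the position effects are drawn

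If both sides of a subject share one layout, position cancels in the within-subject contrast. The simulated ratio is then 1.00–1.01, so nothing is gained.

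**The case against.** The strongest objection is that the response already subtracts baseline, and that the Amendment 6 regression, the only log10 analysis with margins, adjusts for it. Both are true. They confine the point to the ANOVA, but that model alone supports the 6-hour comparison with vehicle: Amendment 6 sets ATE values at 10 and 30 minutes' counterpart times only, namely 10 minutes and 30 seconds.

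A second objection is that the saving is small, and smaller still once pairing is counted. Baseline variation shared by a subject's two sides largely drops out of the contrast, so the relevant SDb is the side-to-side part. This stands, and it makes the upper end of the range less likely.

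A third is that the position layout cannot be seen. The update to the randomisation plan in section 3.3 is redacted and the schedule in Appendix 14.4 is blank. Positions 1–4 are also different places in a 5" × 5" abdominal square and a 1.5" × 5" groin strip, so one shared set of position effects would be misspecified. This stands too, and it is why position is only a secondary step.

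A reader might go further and infer that the intervals are certainly too wide, that side must be in the model because it was balanced, or that the 0.5 and 1.2 margin tests lack baseline adjustment. The documents support none of these. Excess width needs a slope other than 1 or real position effects, and neither is given. A common side shift cancels. The margin tests use a model that contains baseline.

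**Conclusion.** The point holds as a minor one about precision. The ANOVA of log10 change has no baseline covariate and makes no use of the randomised position, so its intervals may be wider than necessary. Under the assumed standard deviations, the current standard error is between 1.00 and 1.33 times the baseline-adjusted one, and 1.01 to 1.09 times at the middle slope. Position could matter if its standard deviation is about 0.2 log10 or more and the two sides differ in layout. Otherwise its terms cost about 1–2% of variance.

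A reader might also infer a validity problem. There is none: extra width is conservative and does not raise the type I error. The primary exact responder-rate intervals and the 267/320 sample size are unaffected.

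**What to change.** 1. In the ANOVA of log10 change in section 8.2.1, add the Treatment Day baseline log10 count as a covariate, with a slope that may differ between abdomen and groin. Keep subject random, and test substance and body area fixed. Apply the same model at each sample time.
2. As a secondary and conditional step, add the positions of the baseline and post-application samples within body area, with side optional. First check on the actual schedule that layouts differ between a subject's two sides.
3. Leave the Amendment 6 regression as stated. At most, report a position-adjusted version as a sensitivity analysis.
4. Amendment 6 itself was issued after testing was complete. Any change made now should be declared as made after testing, and described and justified in the final report as section 8.6 requires.

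The cost is a few lines of text. Baseline counts are already collected, and positions follow from the randomisation schedule. The baseline slopes use 2 degrees of freedom. Position within area uses (3 + 3) × 2 = 12, against 704 × 2 = 1,408 planned sites.

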### **Study Validity**

For a valid study, the active control must make the same objectives that the test article does and both the test article and the active control should be superior to the inactive control for the primary endpoint. The responder rates for both active and inactive treatments at 6 hours are near 100%. Therefore, comparison of responder rates at 6 hours is unlikely to show any difference. Differences in log10 CFU/cm^2 reductions from baseline will be used at 6 hours in order to show that the active treatments are more effective than the inactive control.

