#### Treatment Balance

Each subject will receive two different treatments, one on the right side of the body and one on the left.

The treatment assignments will be balanced such that the number of readings per anatomical site matches the calculated requirements.

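### The pooled log10-reduction ANOVA gives four doubly paired readings one random subject effect, so its product-difference intervals can be too wide or too narrow

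*Combined protocol and SAP*

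**What the plan says.** The model is in the last paragraph of section 8.2.1: "These calculations will use an ANOVA model with subject as a random variable and test substance as a fixed variable". The next sentence puts both areas in the same fit: "Body area (abdomen or groin) will be a fixed variable". The three sample times "will be calculated separately using identical models", and differences in log10 "reductions will be calculated based on the same model". No confidence level is given there; I take 95%.

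On the design, section 3.3 (Treatment Balance) says: "Each subject will receive two different treatments, one on the right side of the body and one on the left". Section 5.1.2.2 puts the assigned products on contralateral areas, and section 8.2.1 counts four sites for a subject with complete data. Each fit therefore holds up to four readings per subject. Section 5.1.2 is less explicit that abdomen and groin on one side get the same product, and the schedule table in Appendix 14.4 is blank in the public copy, so the pairing by side rests on section 3.3.

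On use, Study Validity (sections 3.2 and 6.1) expects responder rates near 100% at 6 hours for active and inactive treatments alike. Section 3.2 therefore says that log10 differences "will be used at 6 hours in order to show that the active treatments are more effective than the inactive control". Section 8.3 sizes the vehicle group partly for that comparison. Section 8.2.1 also makes log10 intervals the fallback when approximate methods for rate differences are unreliable.

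No section or amendment adds a further random term, a covariance structure or a robust variance. Amendment 6 adds a separate regression for average treatment effects and leaves this model in place.

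**The concern.** One random subject effect imposes the same correlation on all six pairs among a subject's four readings. The design gives reason to expect otherwise. Left and right abdomen are the same kind of skin in the same person. Abdomen and groin have different baseline windows (3.0 to 5.5 against 5.0 to 7.5 log10), different application times and different sebaceous character. Two readings on one side also share one application of one product to one half of the body.

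The two departures act in opposite directions. Variation between a subject's body areas cancels out of a left-right product comparison, but the model leaves part of it in the residual, which widens the interval. Variation between a subject's sides does not cancel, but the model counts the two readings on a side as independent replicates, which narrows it. At stake is whether the 6-hour evidence that the actives beat vehicle is judged at its nominal error rate and with the power the data allow.

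**Working it through.** **Plan's own figure.** The plan gives none for this model. The only sample size with visible inputs is 267 per active product (null 70%, alternative 77.8%, power 80%, two-sided 5%). The normal approximation is [(1.96 x sqrt(0.70 x 0.30) + 0.842 x sqrt(0.778 x 0.222)) / 0.078]^2 = 256, or 269 with continuity correction. Exact power at 267 is 82.1%. The figure is reproduced to within 2 subjects and does not depend on the ANOVA.

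**Pair counts.** Section 1.5 gives 320, 320 and 64 readings per area on 352 subjects. With A = ZuraPrep, B = ChloraPrep and C = vehicle: AB + AC = 320, AB + BC = 320, AC + BC = 64. Hence AB = 288, AC = 32, BC = 32, which sum to 352.

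**Algebra.** Let the variances be s (subject), v (subject-by-area), w (subject-by-side) and e (error). For a subject who receives both compared products, take the mean of one side minus the mean of the other.

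- True variance: s and v cancel, each side contributes w, and the four errors contribute 4 x e/4. The total is e + 2w.
- Fitted model: of the six pairs of readings, two share an area and two share a side, so the average covariance is s + (v + w)/3. The residual is (s + v + w + e) - s - (v + w)/3 = e + (2/3)(v + w). The model uses this as the variance of the contrast.

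Model over true variance is [e + (2/3)(v + w)] / [e + 2w]. It equals 1 when v = 2w, which includes both being zero. It exceeds 1 when v > 2w and is below 1 when v < 2w.

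**Numbers for ZuraPrep minus vehicle.** This comparison also draws on the BC pairs and on between-subject information, so I used the full 288/32/32 design with additive product and area terms. With M the equal-correlation covariance and T the true one, the model variance is V = (sum X'M^-1 X)^-1 and the true variance is V (sum X'M^-1 T M^-1 X) V. The false-positive rate is 2 x Phi(-1.96 x model SE / true SE). The shares of total variance are assumptions.

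| Case | s / v / w / e | Model SE | True SE | Ratio | False-positive rate |
|---|---|---|---|---|---|
| (a) | 0.25 / 0.25 / 0 / 0.50 | 0.093 | 0.084 | 1.12 | 2.8% |
| (b) | 0.10 / 0.40 / 0 / 0.50 | 0.097 | 0.083 | 1.16 | 2.3% |
| (c) | 0.25 / 0 / 0.25 / 0.50 | 0.093 | 0.110 | 0.85 | 9.7% |
| (d) | 0.20 / 0.20 / 0.20 / 0.40 | 0.093 | 0.101 | 0.93 | 6.9% |
| v = 2w | 0.30 / 0.20 / 0.10 / 0.40 | 0.090 | 0.090 | 1.00 | 5.0% |

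Simulated random-intercept REML fits gave 2.9%, 2.4%, 10.3% and 6.9% for (a) to (d). More extreme shares widen the range: 0.2/0.4/0/0.4 gives 98.3% coverage of a nominal 95% interval, and 0.2/0/0.4/0.4 gives 87.4%. Small components matter little: 0.3/0.05/0.05/0.6 gives a 5.5% false-positive rate.

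**Power.** At the effect for which the matching model has 80% power, the model as written has 72% in (a) and 68% in (b).

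**Product-by-area term.** Section 8.2.1 does not name one. If it were added and the difference taken within one area, the rates would be 4.0% in (a), 6.5% in (c) and 5.3% in (d). The v = 2w case would move slightly, to 4.7%.

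**Fit within one area.** Each subject then supplies one left-right pair, so one random subject term is enough. Simulated null rejection was 4.8% to 5.7%.

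**The case against.** The strongest reply is that nothing shows the intervals to be wrong. They are correct at v = 2w or with both components zero, and the documents contain no variance components. That stands, and the point is worded accordingly.

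A reader might infer from case (c) that false positives are roughly doubled. The documents do not support that. Case (c) needs a side component as large as the subject component and no area component at all, and nothing in the documents points to a side effect of that size. If area dominates, the interval is conservative; with shares 0.2/0.3/0.1/0.4 the rate is 4.1%.

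The endpoint is change from a baseline taken in the same test area, so a stable difference in flora between areas or sides is largely subtracted. This weakens the mechanism without removing it, because correlated response to a product remains.

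The 80% benchmark for power is a chosen effect. Section 8.3 says at least 40 vehicle readings were needed and 64 were chosen. Suppose 40 gave 80% power, an assumption because the source is redacted. The matching model then has Phi(2.80 x sqrt(64/40) - 1.96) = 94%, and case (a) as written about 91%. The loss is then small.

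Finally, it is tempting to say that a product-by-area fixed term changes nothing. It leaves the covariance structure alone, but as shown it reduces the interval error for area-specific differences in (a), (c) and (d).

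**Conclusion.** The point holds in conditional form. The plan states a model that assumes equal correlation among readings the design pairs in two ways, and nothing relaxes that assumption. For ZuraPrep minus vehicle, the nominal 5% false-positive rate is about 2.3% to 9.7% over cases (a) to (d). The low end is the more plausible direction, so lost precision is a likelier consequence than a false claim. These figures rest on assumed variance shares, the 288/32/32 split, 95% intervals, additive product and area terms, and one product per side.

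A reader might infer that the intervals are known to be wrong, or that the main efficacy claim is in doubt. Neither follows. The primary goal uses exact intervals for responder rates by body area. The required superiority over vehicle concerns the primary endpoint. The 267 comes from a single-proportion calculation, and the Amendment 6 criteria use their own regression by body area. What is affected is the 6-hour active-versus-vehicle log10 comparison, which has no stated margin, and the fallback used when rates lie near 0% or 100%.

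**What to change.** Either of two changes to section 8.2.1 would do, and neither requires knowing the variance components.

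- Fit the log10-reduction model separately within each body area, with test substance fixed and subject random. This is the simpler choice and matches the reporting of responder rates by area.
- Keep the joint model and add random subject-by-area and subject-by-side terms. State whether a product-by-area term is included and whether differences are area-specific or averaged over areas. An unstructured covariance for the four sites is a more general alternative, not an equivalent one: it has 10 parameters against 4 variance components.

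All log10 product differences, including the 6-hour comparison and the fallback, should come from the chosen model. Amendment 6 records that testing is complete, so the change should be reported as a justified deviation under section 8.6, beside the results of the model as written.

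The cost is a sentence or two of plan wording and a refit of existing data. Some intervals may widen if same-side correlation is present, and area-specific fits are less precise than an average over areas.
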